3.3.9. Days of Hospitalization

Duration (in days) of hospitalization will be defined as the number of days subject is hospitalized for COVID-19-related reasons starting from the date of randomization. It will be calculated as the total number of days hospitalized, including readmissions for COVID-19-related reason. See Section 6.5 for the plan for handling subjects who do not have data through Day 29 or die prior to Day 29.

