2.2.3 Baricitinib

2.2.3.1 Potential Risks of Baricitinib

Baricitinib is a Janus kinase (JAK) inhibitor indicated for the treatment of adult patients with moderately to severely active rheumatoid arthritis who have had an inadequate response to one or more TNF antagonist therapies.

The US product labeling indicates a boxed warning for the risk of serious infections, malignancies and thrombosis, while warnings and precautions include serious infections, thrombosis, gastrointestinal perforations, abnormal laboratory assessments (potential changes in lymphocytes, neutrophils, hemoglobin, liver enzymes, and lipids), and avoidance with the use of live vaccines.

The Summary of Product Characteristics (SmPC) indicates as special warning and precautions for infections, including TB, hematological abnormalities, viral reactivation, use of live vaccines, increase in blood lipid parameters, increase in hepatic transaminase, malignancy, venous thromboembolism, hypersensitivity, and use of baricitinib with potent immunosuppressive medications.

Baricitinib has an established safety profile with a positive benefit/risk profile in rheumatoid arthritis. An integrated analysis of patients with active RA exposed to baricitinib with 3770 patients and 10,127 patient years for a maximum exposure of 7 years (as of February 2018) was recently published (38). No significant differences were seen for baricitinib 4-mg vs placebo in adverse events leading to permanent drug discontinuation, death, malignancy, serious infection, or major adverse cardiovascular events. Incidence rates for deep vein thrombosis/pulmonary embolism were numerically higher in baricitinib 4-mg vs placebo; Incidence rates were similar by dose in 2-mg/4-mg-extended dataset. Malignancy (excluding non-melanoma skin cancer) Incidence rates were 0.8 (2-mg) and 1.0 (4-mg; as-randomized analysis). Fewer than 1% of patients discontinued due to abnormal laboratory results. The frequency of Herpes zoster was higher for baricitinib 4-mg vs placebo (1.4 vs 0.4) baricitinib 4-mg vs 2-mg (1.4 vs 1.0).

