Appendix B - ACTT-2: Baricitinib/Remdesivir vs Remdesivir

OBJECTIVES	ENDPOINTS (OUTCOME MEASURES)

 ▪ Incidence and duration of new non-invasive ventilation or high flow oxygen use during the study. 	

 ○ Invasive Mechanical Ventilation / extracorporeal membrane oxygenation (ECMO): 
 ▪ Ventilator / ECMO use up to Day 29. ▪ Incidence and duration of new mechanical ventilation or ECMO use during the study. 	
 • Days of invasive mechanical ventilation/ECMO(if applicable) up to Day 29.

 • Hospitalization 
 ○ Duration of hospitalization (days). 	
 • Days of hospitalization up to Day 29

 • Mortality 
 ○ 14-day mortality ○ 28-day mortality 	
 • Date and cause of death (if applicable)

2. To evaluate the safety of different investigational therapeutics as compared to the control arm as assessed by:
 
 • Cumulative incidence of SAEs through Day 29. • Cumulative incidence of Grade 3 and 4 clinical and/or laboratory AEs through Day 29. • Discontinuation or temporary suspension of study product administrations (for any reason) • Changes in white blood cell (WBC) count with differential, hemoglobin, platelets, creatinine, glucose, total bilirubin, alanine aminotransferase (ALT), aspartate aminotransferase (AST), prothrombin time (PT reported as INR), d-dimer, and C-reactive protein (CRP) over time (analysis of lab values in addition to AEs noted above). 	
 • SAEs • Grade 3 and 4 AEs • WBC with differential, hemoglobin, platelets, creatinine, glucose, total bilirubin, ALT, AST, INR, d-dimer, CRP on Day 1; Days 3, 5, 8, and 11 (while hospitalized); and Days 15 and 29 (if attends in-person visit or still hospitalized).
Exploratory	

To evaluate the virologic efficacy of different investigational therapeutics as compared to the control arm as assessed by:
	

OBJECTIVES	ENDPOINTS (OUTCOME MEASURES)

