3. STUDY OBJECTIVES AND ENDPOINTS

3.1. Study Objectives

Primary Objective

To evaluate the clinical efficacy, as assessed by time to recovery, of different investigational therapeutics as compared to the control arm.

Secondary Objectives

The key secondary objective is to evaluate the clinical efficacy of different investigational therapeutics relative to the control arm in adults hospitalized with COVID-19 according to clinical status (8-point ordinal clinical scale) at Day 15.

The other secondary objectives are to:

1. Evaluate clinical efficacy of different investigational therapeutics as compared to the control arm as assessed by:
 - Clinical Severity
 - 8-Point Clinical Status Ordinal scale:
 - Time to an improvement of one category and two categories from Day 1 (baseline) on the clinical status 8-point ordinal scale.
 - Subject clinical status using 8-point ordinal scale at Days 3, 5, 8, 11, 15, 22, and 29.
 - Mean change in the clinical status 8-point ordinal scale from Day 1 to Days 3, 5, 8, 11, 15, and 29.
 - National Early Warning Score (NEWS):
 - Time to discharge or to a NEWS of ≤ 2 and maintained for 24 hours, whichever occurs first.
 - Change from Day 1 to Days 3, 5, 8, 11, 15, and 29 in NEWS.
 - Oxygenation:
 - Oxygenation use up to Day 29.
 - Incidence and duration of new oxygen use through Day 29.
 - Non-invasive ventilation/high flow oxygen:
 - Non-invasive ventilation/high flow oxygen use up to Day 29.
 - Incidence and duration of new non-invasive ventilation or high flow oxygen use through Day 29.
 - Invasive Mechanical Ventilation / extracorporeal membrane oxygenation (ECMO):
 - Ventilator/ECMO use up to Day 29.
 - Incidence and duration of new mechanical ventilation or ECMO use through Day 29.

- Hospitalization
 - Duration of hospitalization (in days) through Day 29.
 - Mortality
 - 14-day mortality.
 - 28-day mortality.
2. Evaluate the safety of the intervention through 28 days of follow-up as compared to the control arm as assessed by:
- Cumulative incidence of SAEs through Day 29
 - Cumulative incidence of Grade 3 and 4 clinical and/or laboratory AEs through Day 29.
 - Discontinuation or temporary suspension of study product administrations (for any reason).

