3.2. Endpoints

Primary Endpoint

Time to recovery, where recovery is defined as clinical status in states 1, 2, or 3 of the 8-point ordinal scale, censored at Day 29.

- Clinical status of a subject (8-point ordinal scale) is defined below:
 - 8. Death;
 - 7. Hospitalized, on invasive mechanical ventilation or ECMO;
 - 6. Hospitalized, on non-invasive ventilation or high flow oxygen devices;
 - 5. Hospitalized, requiring supplemental oxygen;
 - 4. Hospitalized, not requiring supplemental oxygen - requiring ongoing medical care (COVID-19 related or otherwise);

3. Hospitalized, not requiring supplemental oxygen - no longer requiring ongoing medical care;
2. Not hospitalized, limitation on activities and/or requiring home oxygen;
1. Not hospitalized, no limitations on activities

Secondary Endpoints

The key secondary endpoint is clinical status (8-point ordinal scale) on Day 15.

The other secondary endpoints are:

- Ordinal outcome assessed daily while hospitalized and on Days 15, 22, and 29.
- NEWS assessed daily while hospitalized and on Days 15 and 29.
- Days of supplemental oxygen (if applicable).
- Days of non-invasive ventilation/high-flow oxygen (if applicable).
- Days of invasive mechanical ventilation/ECMO (if applicable).
- Days of hospitalization.
- Date and cause of death (if applicable).
- SAEs.
- Grade 3 and 4 adverse events
- WBC with differentials, hemoglobin, platelets, creatinine, glucose, total bilirubin, ALT, AST, INR, d-dimer, and CRP on Day 1; Days 3, 5, 8, and 11 (while hospitalized); and Days 15 and 29 (if attends in-person visit or still hospitalized).

Exploratory Endpoint

- Qualitative and quantitative polymerase chain reaction PCR for SARS-CoV-2 in OP swab on Day 1; Days 3, 5, 8, and 11 (while hospitalized); and Days 15 and 29 (if attends in-person visit or still hospitalized).
- Qualitative and quantitative PCR for SARS-CoV-2 in blood on Day 1; Days 3, 5, 8, and 11 (while hospitalized).

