8.2.9. Days of Hospitalization

Duration of hospitalization days will be summarized in a table using medians and quartiles by treatment arm. Incidence of readmittance will also be summarized ([Table 48](#)). Analyses will be performed in the ITT and As Treated population. Bee swarm plots of days hospitalized by treatment arm will be generated, where subjects whose days are imputed to the maximum of 28 days due to death are grouped separately from subjects who do not die.

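### The SAP limits hospital readmission days and readmittance to COVID-19-related causes, although the protocol endpoint has no cause limit, with no attribution rule and no all-cause version

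*SAP*

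**What the plan says.** Protocol Appendix B, Section 3 (Objectives and Endpoints) gives the endpoint as "Days of hospitalization up to Day 29" and does not qualify it by cause. The SAP at first follows this. Its objective in 3.1 is "Duration of hospitalization (in days) through Day 29" and its endpoint list in 3.2 has "Days of hospitalization", both unqualified.

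The derivation in SAP 3.3.9 is narrower. Its first sentence defines the duration as "the number of days subject is hospitalized for COVID-19-related reasons starting from the date of randomization". Its second says: "It will be calculated as the total number of days hospitalized, including readmissions for COVID-19-related reason".

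SAP 8.2.9 summarizes the duration by medians and quartiles in each arm and adds "Incidence of readmittance will also be summarized". That section states no cause limit. The limit on incidence comes from SAP Section 15, where the list of changes from version 2.0 to 3.0 records, as a clarification applying throughout, that only COVID-19 readmittances enter analyses using readmittance. The Table 48 shell has a block for days and a block for incidence of readmittance. Its footnotes define N, the quartiles and the denominator, and say nothing about cause.

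**The concern.** A protocol endpoint that counts every hospital day has been narrowed in the derivation without a stated reason. The cause of a readmission is itself an outcome after randomization, and treatment can affect it. If the arms differ in readmissions for other causes, removing those readmissions removes part of a real difference between arms, even when each judgement of cause is made blind.

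The question is not remote for this drug. Protocol Appendix B, 2.2.3.1 notes: "The US product labeling indicates a boxed warning for the risk of serious infections, malignancies and thrombosis". A readmission for infection or a clot could reasonably be classed as COVID-19-related or not, and neither document says who decides or by what criterion. Two teams working from the same SAP could produce different versions of Table 48, and a reader of that table would take either version as all-cause.

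**Working it through.** No sample size, event count or error rate in the plan depends on this point, so there is no plan figure to reproduce. The check has three parts.

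**1. Definitions side by side**

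| Place | First stay | Readmissions |
|---|---|---|
| Protocol App. B, Section 3 | all days | all days |
| SAP 3.1 and 3.2 | all days | all days |
| SAP 3.3.9, first sentence | COVID-19-related days only | COVID-19-related days only |
| SAP 3.3.9, second sentence | total days | COVID-19-related only |
| SAP 15, version 3.0 changes | not addressed | COVID-19 reasons only |
| SAP 8.2.9 and Table 48 shell | no limit stated | no limit stated |

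For readmissions, the exclusion in 3.3.9 is explicit and Section 15 shows that it is intended. For the first stay, the two sentences of 3.3.9 conflict.

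**2. Fit with neighbouring rules**

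- Days of oxygen and of ventilation (SAP 3.3.6 to 3.3.8) carry no cause limit. On its face, a subject readmitted with a pulmonary embolism could accrue oxygen days but no hospital days.
- Death while hospitalized is imputed as 28 days whatever its cause (SAP 6.5), so the gap concerns non-fatal readmissions.
- Follow-up contacts ask about readmission without limiting cause (Protocol App. B, 1.2, note 9).
- The Table 22 notes say that readmission there means readmission for COVID-19. Table 48 has no such note.

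**3. Size, with assumed inputs**

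Simple arithmetic first. Assume COVID-19 readmissions of 2% in both arms and other readmissions of 3% versus 1%, each lasting 7 days. Restricted reporting shows 2% versus 2%; all-cause reporting shows 5% versus 3%. Omitted days per subject are 0.03 × 7 = 0.21 and 0.01 × 7 = 0.07, a difference in means of 0.14 day. With 1032/2 = 516 per arm, about 15 versus 5 readmitted subjects would be missing (0.03 × 516 = 15.5; 0.01 × 516 = 5.2). Swapping the two rates reverses the sign.

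The plan reports medians and quartiles, so a simulation was also run for a single arm of 516. The first stay was log-normal (median 8 days, log-scale SD 0.7), rounded up and capped at 28, with 2,000 repetitions. A share of subjects was given an added non-COVID readmission, with the total again capped at 28. The figures are the amounts by which the restricted summary falls short of the all-cause one.

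| Readmitted | Days each | Mean | Median | Q3 | Patient-days per arm |
|---|---|---|---|---|---|
| 2% | 3 | 0.06 | 0.09 | 0.08 | 30 |
| 2% | 7 | 0.13 | 0.18 | 0.25 | 67 |
| 2% | 14 | 0.25 | 0.18 | 0.46 | 130 |
| 5% | 3 | 0.14 | 0.23 | 0.20 | 74 |
| 5% | 7 | 0.33 | 0.40 | 0.60 | 170 |
| 5% | 14 | 0.63 | 0.39 | 1.23 | 325 |
| 10% | 3 | 0.29 | 0.41 | 0.38 | 148 |
| 10% | 7 | 0.66 | 0.79 | 1.12 | 340 |
| 10% | 14 | 1.25 | 0.80 | 2.79 | 645 |

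The effect on a comparison is the difference between two rows. For 5% versus 2% at 7 days it is 0.33 − 0.13 = 0.20 day in the mean, 0.40 − 0.18 = 0.22 in the median and 0.60 − 0.25 = 0.35 in Q3. Equal rates and lengths give no expected difference. The simulation ignores the gap between discharge and readmission, so it tends to overstate the loss.

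**The case against.** The strongest reply is that little is lost. Hospitalization or its prolongation is an SAE criterion (Protocol App. B, 8.3.2), and any venous thromboembolism is reportable (8.3.1). SAE rates are compared between arms, infections have Tables 74 to 79, and SAEs enter the composite safety endpoint (SAP 3.3.11 and 9.4). The ordinal scale counts hospital care whatever its cause. The endpoint is one of many secondaries, is descriptive, and lies outside multiplicity control (SAP 6.8). The restriction was deliberate, was recorded, and matches the readmission sensitivity analysis in SAP 3.3.2.

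Most of this stands, and it rules out a reading that the plan hides these harms. It does not supply the missing comparison. SAE rates count a subject once, the composite stops at the first event, and the reason an event was serious appears only in listings. No planned table compares all-cause readmission or all-cause hospital days by arm. Recording a restriction does not explain why it departs from the protocol endpoint.

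It is also fair to say that an attribution procedure may exist elsewhere, because Protocol App. B, 7.4 sends data collection after readmission to the manual of procedures, which is not among these documents.

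**Conclusion.** The point holds for readmissions. SAP 3.3.9, read with Section 15, leaves non-fatal readmissions for other causes out of the hospital-days endpoint and out of the incidence of readmittance. It does so against the protocol endpoint, without an attribution rule in these documents, without an all-cause version, and without disclosure in Table 48. The incidence comparison is the more exposed of the two. Under the assumed inputs above, median days move by less than one day in an arm. The primary and key secondary results do not depend on this definition.

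A reader might infer more, and the documents do not support it:

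- *First-stay days spent on a drug complication are removed.* This is possible under the first sentence of 3.3.9, but the second sentence counts total days. It is an ambiguity, not an established loss.
- *The restriction favours baricitinib.* The direction is not fixed. Protocol App. B, 2.2.3.1 reports, for rheumatoid arthritis, no significant difference from placebo in serious infection and numerically more thrombosis. It treats the drug's effect on clots in COVID-19 as unknown, and it notes that the infection itself raises clot risk, so clots may well be classed as COVID-19-related.
- *Cause is judged unblinded.* The oral product is blinded (Protocol App. B, 6.3.2). The weakness is an unspecified rule applied to an outcome after randomization.
- *The trial loses its measure of net benefit.* The documents present hospital days as an efficacy descriptor and evaluate safety separately.

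**What to change.** - In SAP 3.3.9 and 8.2.9, Tables 48 and 49 and Figure 36, define days of hospitalization and readmittance as all-cause from randomization to Day 29, matching the protocol.
- Rewrite the two sentences of 3.3.9 so that they agree on the first stay.
- Keep the COVID-19-related version as a labelled supplementary row. State who attributes cause, by what criterion, and that this is done blind to arm.
- If the sponsor prefers to keep the restriction as the main version, justify it as a change from the protocol endpoint, footnote Tables 48 and 49, and add an all-cause readmittance row.

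The cost is SAP wording, one derivation and one extra table row, plus a check that the forms capture dates for every readmission. The downside is that some admissions unrelated to drug or disease will be counted; with randomization these should be similar in both arms.

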3.3.10. Time to Death

For analysis of time to death, the time to death will be defined as the elapsed time (in days) from randomization (or treatment administration for the safety analysis) to death. Any subjects that are lost to follow-up or terminated early prior to death will be censored at the day of their last observed assessment or last captured event (e.g. the end date of an adverse event). If it is learned that a subject who terminated early had subsequently died prior to Day 29, then the subject will be classified as dead. Subjects who complete follow-up will be censored at the earliest of their Day 29 visit and (actual) Day 29. Deaths that occur after Day 29 will be censored at Day 29.

Similar censoring methods will be used for the 14-day mortality analyses in that deaths that occur after Day 15 will be censored at Day 15 and subjects who are confirmed alive through Day 15 will be censored at Day 15. Subjects whose last observed assessment or last capture event (e.g. the end date of an adverse event) is prior to Day 15 will be censored at that last observed assessment/event.

3.3.11. Composite Endpoint of Death, SAEs, Severe AEs, Discontinuation of Study Product Administrations

A safety composite endpoint will be defined as the occurrence of at least one of the following through Day 29:

1. Death

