7.2 Withdrawal from the Study

Subjects are free to withdraw from participation in the study at any time upon request, without any consequence. Subjects should be listed as having withdrawn consent only when they no longer wish to participate in the study and no longer authorize the Investigators to make efforts to continue to obtain their outcome data.

Subjects who withdraw from this study or are lost to follow-up after signing the informed consent form (ICF) and administration of the study product, will not be replaced. The reason for subject withdrawal from the study will be recorded on the appropriate CRF.

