9.4. Deaths, Serious Adverse Events and other Significant Adverse Events

Listings of death and other serious adverse events will be presented, including Subject ID, treatment group, Adverse Event Description, Number of Days Post Dose (Duration), Number of Days Post Dose the Event Became Serious, Reason Reported as an SAE, Severity, Relationship

to Treatment, Alternate Etiology if not Related, Action Taken with Study Treatment, Subject Discontinuation, Outcome, MedDRA SOC, and MedDRA PT (Listing 14 and Listing 16).

The number of subjects who die by Day 15 and Day 29 will be presented by treatment arm. The 14- and 28-day mortality rate, which will use Kaplan-Meier estimator, will be presented (Table 64).

Mortality through Day 15 and 29 will also be analyzed as a time to event endpoint (see Section 3.3). A table will present median time to event along with 95% confidence intervals overall for each treatment arm along with the hazard ratio estimate and log rank p-values (Table 66). Differences in time-to-event endpoints by treatment will be summarized with Kaplan-Meier curves (Figure 44). Analyses of mortality will be performed in the ITT and the Treated analysis populations. As a supplemental analysis, a Cox model will be fit with binary indicators for treatment group and disease severity as well as a treatment * disease severity interaction term. The model will be fit in the ITT and Treated analysis populations. The treatment group hazard ratios and CIs and the interaction term p-value will be reported. Finally, the results of the sensitivity time-to event analysis described in Section 6.4 will be presented in a table; the same summaries as in Table 66 will be provided. As requested by the DSMB, a restricted mean survival time analysis of mortality will be performed as an exploratory analysis. The restricted mean mortality time estimates will be provided for each treatment group and randomized disease severity stratum as well as the difference in restricted mean recovery time between treatment groups within each of the severity strata (Table 72).

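### The 28-day mortality rule counts deaths learned of after early termination but gives no matching credit to terminators known to be alive, so censoring depends on the outcome

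*SAP*

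**What the plan says.** SAP 3.3.10 measures death from randomization: "the time to death will be defined as the elapsed time (in days) from randomization". Subjects lost to follow-up or terminated early before death "will be censored at the day of their last observed assessment or last captured event"; the SAP's example of such an event is the end date of an adverse event. An exception follows for early terminators only: "If it is learned that a subject who terminated early had subsequently died prior to Day 29, then the subject will be classified as dead". For the others, "Subjects who complete follow-up will be censored at the earliest of their Day 29 visit and (actual) Day 29".

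The next paragraph says similar methods apply to 14-day mortality, and adds that "subjects who are confirmed alive through Day 15 will be censored at Day 15". Its closing sentence then censors anyone whose last assessment or captured event falls before Day 15 at that earlier date.

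SAP 9.4 names the estimator: "The 14- and 28-day mortality rate, which will use Kaplan-Meier estimator, will be presented" (Tables 64 and 65). Hazard ratios and log-rank p-values follow in Tables 66 and 67.

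Protocol Appendix B 7.2 lists a subject as having withdrawn consent only when that person no longer wishes to take part and "no longer authorize the Investigators to make efforts to continue to obtain their outcome data".

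**The concern.** Kaplan-Meier estimation requires that leaving the risk set carry no information about the outcome. Take two subjects who terminate on Day 8 with nothing captured afterwards. One is later learned to have died on Day 20; that subject stays at risk to Day 20 and counts as an event. The other is known to be alive on Day 29; as the 28-day rule is written, that subject is censored at Day 8. The death enters the numerator while the comparable survivor leaves the denominator.

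Mortality at 14 and 28 days is a named secondary outcome. If the arms differ in how many subjects terminate, or in how completely later deaths come to light, the asymmetry also reaches the hazard ratio.

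**Working it through.** **Inputs from the documents.** Neither document gives a mortality assumption or an early-termination rate for this stage, so there is no plan figure for this point to reproduce. Arm size comes from SAP 5: 4 × (1.96 + 1.04)² / (ln 1.25)² = 723 recoveries; 723 / 0.70 = 1032.9, stated as 1032; 1032 / 2 = 516 per arm. Mortality levels of 8.0% and 11.6% are the preliminary results of the first stage (SAP 2).

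**Assumptions.** Early termination d of 2%, 5% or 10%, spread evenly over Days 1–21; constant daily hazard to Day 28; a share p of later deaths learned of; terminators' hazard after leaving equal to hr times that of the others; no survivor event captured after termination.

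**Hand example.** An arm of 516 has 26 terminators at Day 5, of whom 2 are later learned to have died. There are 41 deaths in all, every one after Day 5. With no censoring between Day 5 and Day 28, Kaplan-Meier reduces to a proportion.
- SAP rule: the 24 surviving terminators leave, so 41 / (516 − 24) = 41 / 492 = 8.33%.
- Same rule for deaths and survivors, all traced: 41 / 516 = 7.95%.
- All 26 censored at Day 5: 39 / 490 = 7.96%.

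The two consistent rules nearly agree; the mixed rule is about 0.4 points higher.

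**Large-sample limit, hr = 1, p = 1.** On day t the estimated hazard is h / [1 − d·F(t−1)·S(28)/S(t−1)]. Here h is the true daily hazard, F the share of terminations that have already happened, and S the survival function. The average of F(t−1) over Days 1–28 is 17/28 = 0.607, so the increase is roughly (1 − m) × [−ln(1 − m)] × d × 0.607. At m = 8%, d = 5%: 0.92 × 0.0834 × 0.05 × 0.607 = 0.0023, or 0.23 points. The full calculation gives:

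| True 28-day mortality | d = 2% | d = 5% | d = 10% |
|---|---|---|---|
| 8.0% | 8.09% (+0.09) | 8.24% (+0.24) | 8.49% (+0.49) |
| 11.6% | +0.13 | +0.33 | +0.69 |

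With p = 0 and hr = 1 the error is zero, and with complete vital status applied to deaths and survivors alike the estimate is 8.00%. The one-sided exception is therefore the source.

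**When ascertainment is partial.** Error in points against true mortality, with 8% mortality in non-terminators and d = 10%:

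| hr | p = 0.25 | p = 0.5 | p = 1 |
|---|---|---|---|
| 1 | +0.12 | +0.25 | +0.49 |
| 2 | −0.21 | +0.02 | +0.50 |
| 4 | −0.84 | −0.39 | +0.50 |

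For hr above 1 the net error is upward only if p exceeds about 1 − 1/hr, that is 0.5 for hr = 2 and 0.75 for hr = 4.

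**Arm comparison.** Suppose 5% terminate in both arms, the drug has no effect, and later deaths are learned in one arm only. The hazard ratio is then about ln(1 − 0.0824) / ln(1 − 0.0800) = 1.03. It is 1.01 at 2% termination and 1.06 at 10%.

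**Scale.** At 8% mortality and 516 per arm, the standard error of one arm's rate is √(0.08 × 0.92 / 516) = 1.2 points, and of the difference 1.7 points.

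**Day 15 text.** Take a subject who terminates on Day 8 with no later captured event and is then confirmed alive past Day 15. One sentence censors this subject at Day 15, the other at Day 8. Both apply.

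**The case against.** Three stronger readings are tempting, and the documents do not support them.

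- *Time after termination counts only if it ends in death.* The last-captured-event clause can extend a survivor's follow-up, since Protocol Appendix B 8.3.2 has serious adverse events followed until they resolve or stabilise. That limits the asymmetry without removing it: credit needs a captured event, and knowing the subject is alive is not one.
- *The reported rates are necessarily too high.* If terminators are sicker and their deaths only partly traced, the rate can still be too low, as the second table shows.
- *The treatment comparison is biased.* With similar termination and ascertainment in both arms the error largely cancels, and the baricitinib component is blinded. No figure in the documents suggests a difference between arms.

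The rest of the defence has force. Few subjects should be affected: stopping study drug is not leaving the study (Appendix B 7.1.1), lost subjects must be pursued (7.3), and telephone visits on Days 15, 22 and 29 already ask about mortality. Active tracing is closed for those who have refused outcome collection. Counting known deaths can be called conservative. The 14-day paragraph's reference to similar methods hints at a known-alive rule for Day 29 as well. But a hint is not a rule a programmer can apply, and the 14-day text it would be borrowed from conflicts with itself.

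**Conclusion.** The asymmetry is in the written 28-day rule, and following that rule moves the Kaplan-Meier rate up relative to either consistent alternative. Whether the result is also too high against true mortality is conditional. It is if all later deaths are learned, or if some are and terminators' risk is no higher than that of other subjects; otherwise the sign is uncertain.

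The size is modest: about 0.1–0.5 points at 8% mortality with 2–10% early termination, all later deaths learned and equal hazard. These rates are assumptions. Even 0.5 points is well under one standard error of an arm's rate, so this is a matter of stating a sound estimator and does not threaten the trial's conclusions. The 14-day conflict needs resolving whatever its numerical effect.

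**What to change.** Rewrite the censoring text in SAP 3.3.10 as one rule for all early-terminated and lost subjects; the learned-death sentence currently omits the lost. Count deaths, and censor survivors at the last date known alive, drawing on the same sources for both and capping at Day 15 or Day 29. Use existing contacts and records for those who have not refused outcome collection. Replace the two competing Day 15 sentences with this rule.

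Add a sensitivity analysis that censors every such subject at termination, including those later learned to have died, and report by arm how many terminated early and how many had vital status established.

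The cost is a short SAP edit, one extra run of the mortality tables, and a record or telephone check for a small number of subjects. Some will not be traced, and if deaths are easier to find than survival, outcome-dependent ascertainment will partly remain. The sensitivity analysis may understate mortality if terminators are sicker, so the two results should be read together.
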